5.9. Analysis of Genomics Variables

Plans for the analysis of genomics data will be provided in a separate SAP.

6. DATA CONVENTIONS

The following analysis conventions will be used in the statistical analysis.

6.1. Definition of Baseline for Efficacy and Safety Variables

Unless otherwise specified, the baseline value is generally defined as the baseline value in the neurocognitive function study (R727-CL-1532), i.e., the last available value before the first dose of double-blind study treatment in that study.

In addition to the OLE study database, some data will be recovered from the neurocognitive function study (R727-CL-1532) database

6.2. General Data Handling Conventions

In general, the following formulas will be used for computation of parameters:

Time from diagnosis

Time from diagnosis (years) = (Date of informed consent – Date of diagnosis*) / 365.25.

(*):In case the month of diagnosis would be missing, it will be put equal to JANUARY if the year of diagnosis equals the year of informed consent; it will be put equal to JUNE otherwise. In the case the day is missing, the day will be put equal to 1st if the month and year of diagnosis equals the month and year of informed consent; otherwise it will be put equal to the 15th of the month.

Date of last dose of study treatment

The date of the last injection is equal to the last date of administration reported on injection administration case report form page, or missing if the last administration date is unknown.

Renal function formulas

Estimated GFR will be derived using the Modification of the Diet in Renal Disease (MDRD) equation:

186.3 × (creatinine in μ mol/L / 88.4)^{-1.154} × (age in years)^{-0.203} (x 0.742 if female, x 1.21 if race is "black or African American").

Lipids variables, laboratory safety variables, hs-CRP

For data below the lower limit of quantification (LLOQ) / limit of linearity, half of the lower limit value (i.e., LLOQ/2) will be used for quantitative analyses. For data above the upper limit of quantification (ULOQ) / limit of linearity, the upper limit value (i.e., ULOQ) will be used for quantitative analyses.

6.3. General Missing Data Conventions

For categorical variables, patients with missing data are not included in calculations of percentages unless otherwise specified. When relevant, the number of patients with missing data is presented.

Handling of baseline definition if "time" of first study treatment administration or time of assessment at week 0 visit is missing

If the time of the first study treatment administration or the time of assessment at week 0 visit is missing, then the baseline value is defined as the last available value obtained before or on the day of the first study treatment administration.

Handling of computation of treatment duration and compliance if study treatment first or end of treatment date is missing

If the last or first injection date is missing, the exposure duration and compliance will be left as missing.

Handling of safety and efficacy analysis periods and survival analysis if end of study treatment date is missing

If the last injection date is missing, then this date is imputed to the earliest between:

- the last day of the month and year, when applicable or else the 31st of December of the year,
- the date of the end of treatment visit (week 96 visit for completer, early end of treatment visit for patients who prematurely discontinued the study treatment),
- the date of the last contact

for the purpose of safety and efficacy analysis period start and/or end.

Handling of medication missing/partial dates

No imputation of medication start/end dates or times will be performed. If a medication date or time is missing or partially missing and it cannot be determined whether it was taken prior or concomitantly, it will be considered a prior, concomitant, and post-treatment medication.

Handling of adverse events with missing or partial date/time of onset, worsening, seriousness

Missing or partial AE dates and times will be imputed so that if the partial AE date/time information does not indicate that the AE started prior to treatment or after the TEAE period, the AE will be classified as treatment-emergent. These data imputations are for categorization

purpose only and will not be used in listings. No imputation is planned for date/time of AE resolution.

Handling of adverse events when date and time of first study treatment administration is missing

When the time of the first study treatment administration is missing, all AEs that occurred on the day of the first study treatment administration will be considered as treatment-emergent AEs.

Handling of missing assessment of relationship of adverse events to investigational medicinal product

If the assessment of the relationship to study treatment is missing, then the relationship to study treatment has to be assumed as possibly related in the frequency tables, but no imputation should be done at the data level.

Handling of potentially clinically significant abnormalities

If a patient has a missing baseline value he will be grouped in the category "normal/missing at baseline."

For PCSAs with 2 conditions, one based on a change from baseline value and the other on a threshold value or a normal range, with the first condition being missing, the PCSA will be based only on the second condition.

For a PCSA defined on a threshold and/or a normal range, this PCSA will be derived using this threshold if the normal range is missing; e.g., for eosinophils the PCSA is >0.5 GIGA/L or >ULN if ULN \geq 0.5 GIGA/L. When ULN is missing, the value 0.5 should be used.

Measurements flagged as invalid by the laboratory will not be summarized or taken into account in the computation of PCSA values.

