## 7.5.4. Treatment Compliance

Patients will complete a dosing log to document compliance with study drug administration. Measures taken to ensure and document study drug accountability and compliance are as follows:

- The investigator or designee will obtain, via IVRS/IWRS, the treatment kit number(s) and will dispense the treatment kit(s) to the patient.
- Accountability is to be verified during study drug kit re-supply visits only. The used and unused kit(s) should be brought to these visits for accountability purposes.
- All kits, including used and unused kits, are to be returned by the patient at the designated visit. An unused kit contains the unused auto-injector.

- All sharps containers should be returned to the site by the patient.
- The investigator/study coordinator will enter data in the appropriate CRF pages, according to data recorded in the treatment log form.
- The monitor will check the data consistency among CRF pages, treatment log form and returned unused kit(s).

All treatments kits will be retrieved by the sponsor. A detailed treatment log of the returned study drug will be established with the investigator or designee and countersigned by the investigator and the monitoring team.

All drug compliance records must be kept current and made available for inspection by the sponsor and regulatory agency inspectors.

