#### Table 1:Schedule of Events

						_					End of Treatment/Early Termination/
	Treatment Period								End of Study 		
Study Procedure	Visit 1	Visit 2	Visit 3	Visit 4	Visit 5	Visit 6	Visit 7	Visit 8	Visit 9	Visit 10	Visit 11
Day	1										
Week	0	8	12	24	48	72	96	120	144	168	192
Visit Window (days)		±3	±3	±3	±3	±3	±3	±3	±3	±3	±3
Screening/Baseline:											
Inclusion/Exclusion	X										
Informed Consent	Х										
Demographics	Х										
Prior Medication History	Х										
IVRS/IWRS	Х	X	Х	Х	Х	Х	Х	Х	Х	Х	
Treatment:											
Review of Diet	X	X	X	Х	X	X	X	Х	Х	X	X
Administer Study Drug	X 										
Study Drug Kit Dispensation 	Х	Х	X	Х	X	X	Х	Х	Х	X	
Concomitant Medication 	Х	Х	Х	Х	X	Х	Х	Х	Х	X	Х
Patient Drug Log Dispensation/Collection	Х	X	X	Х	Х	Х	Х	Х	Х	X	Х
Safety:											
Vital Signs	Х				X		X		X		X
Physical Examination and Body Weight	Х				Х		Х		Х		Х
Adverse Events	Х	Х	Х	Х	Х	Х	Х	Х	Х	Х	Х
Efficacy:											
Total-C, LDL-C, HDL- C, TG, non-HDL-C 	X 	X		X	X	X	X	Х	Х	X	X
Apo B, Apo A-1, Lp(a)	X 				Х		Х		Х		Х
Laboratory Testing:											
Hematology	X 			Х	X	Х	Х	Х	Х	X	X

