2.3. Study Plan

From week 8 in the OLE study, lipid measurements will be collected and will be known by the investigator in real time. The investigator will manage the PRALUENT dose at his/her discretion based on LDL-C levels, starting at week 12, by either modifying the dose from 75 mg Q2W to 150 mg Q2W, maintaining the dose, modifying the dose from 150 mg Q2W to 75 mg Q2W, or discontinuing treatment with PRALUENT at any time during the treatment period. If a dose is missed, the patient should administer the injection as soon as possible and thereafter resume treatment from the day of the missed dose (ie, resume on the next originally

planned date). The statin dose should not be modified to adjust the degree of LDL-C lowering.

Background LMT will be prescribed as per clinical practice and should remain the same as in the neurocognitive function study (R727-CL-1532). Lipid modifying therapy, including statins, should not be changed during the course of the study. However, if clinically necessary, background LMT may be adjusted at the investigator's discretion. Any adjustment will be documented in the electronic case report form (CRF). Patients not treated with a statin (eg, statin intolerant patients, or patients in whom statin treatment was stopped during the neurocognitive function study [R727 CL 1532] for a safety reason) may still participate in the OLE study.

The investigator should refer to the label for information on PRALUENT and other LMTs.

Patients should continue a National Cholesterol Education Program-Adult Treatment Panel III Therapeutic Lifestyle Changes (NCEP-ATPIII TLC) diet or equivalent throughout the entire study duration.

Visits are planned at weeks 0, 8, 12, 24, 48, 72, 96, 120, 144, 168, and 192. At each visit, except at the EOS visit at week 192, study drug will be dispensed to the patient. If at any time during the study after the week 8 visit, the investigator, based on lipid results or safety issues, decides to modify the dose of PRALUENT, an unscheduled kit dispensation visit will be performed.

Figure 1: Study Flow Diagram

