4.4. Patient Disposition

Patient disposition includes the description of patient status at major milestone decisions in the study, as well as the patient analysis populations.

For patient study status, the following milestone categories are defined below. For all categories of patients, percentages will be calculated using the number of enrolled patients as the denominator, with two exceptions. Specifically, the two exceptions are for the screened and non-enrolled categories, which will not have associated percentages shown.

- Enrolled patients: met the inclusion criteria regarding the target indication and signed the informed consent form (ICF)
- Enrolled but not treated patients
- Enrolled and treated patients
- Patients complete 192 weeks of open-label treatment period (at least 190 weeks of exposure and visit W192 performed)
- Patients completed the study treatment period (i.e. as collected on the End of Open-Label Treatment eCRF)
- Patients who did not complete the study treatment period and patient's decision for treatment period discontinuation (as per the End of Open-Label Treatment eCRF)
- Patients who discontinued study treatment by main reason for permanent treatment discontinuation (as per the End of Open-label Treatment eCRF)
- Patients completed the study (i.e. as collected on the Study Completion eCRF)
- Patients who early terminated the study (as per the Study Completion eCRF)
- Patients who early terminated the study by main reason for early termination (as per the Study Completion eCRF)
- Status at last study contact
- Subject's visit impact due to COVID-19
- Study/Treatment discontinuation due to COVID-19

As defined in Section 3 of this document, the patient analysis populations are:

• Safety Population (SAF)

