- For quantitative safety parameters including central laboratory measurements and vital sign scores, descriptive statistics will be used to summarize results and change from baseline values by visit, the last on-treatment value and the worst on-treatment value. The last on-treatment value is defined as the last post-baseline value collected during the respective treatment period (as defined in Section 4.7.1). The worst on-treatment value is defined post-baseline as the nadir and/or the peak value collected during the respective treatment period, according to the direction (minimum or maximum) of the abnormality as defined in the PCSA list.
- Analyses performed according to diabetes status will be done considering diabetic patients as patients with either type 1 or type 2 diabetes in the medical history e-CRF page (regardless of the ongoing status) in the neurocognitive function study (R727-CL-1532).

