5.7.2. Analysis of Clinical Laboratory Variables

Clinical laboratory parameter actual values (quantitative) and change from baseline values will be descriptively summarized at baseline and each post-baseline visit (collected up to the day of last dose of study treatment +21 days) by at least patient number, mean, median, Q1, Q3, SD, minimum and maximum for each patient group. Additionally, laboratory parameter measures for last on-treatment values and worst on-treatment values will be summarized in a similar manner. Clinical laboratory parameters mean changes from baseline, with the corresponding SE, can be plotted at each visit, in the case results warrant further investigation. These parameters will be presented by the biological functions defined in Section 4.7.2. For glucose, only fasting samples will be included in the summaries.

Individual patient laboratory parameter measurements will be additionally evaluated by PCSA criteria, specifically identifying patients with at least one post-baseline measurement that meets the PCSA criteria within the TEAE period. The following additional project specific PCSA criteria will also be evaluated during the TEAE period:

- Patients with a hemoglobin decrease from baseline ≥ 15 g/L.
- Patients meeting the ALT increase defined in Section 4.7.1.2.
- Glucose (quantitative summary and PCSA) will also be analyzed, overall and according to the diabetic status at baseline.

Patients meeting the PCSA criteria at least once will be summarized by patient count (and percent) for a post-baseline PCSA measurement while accounting for the baseline PCSA status (PSCA normal/missing; PCSA abnormal), for each patient group. For the appendix, this laboratory parameter PCSA table will be reproduced with patients meeting the PCSA criteria at least once during the TEAE period regardless of baseline PCSA status. These laboratory parameters will be presented by the biological functions defined in Section 4.7.2. Patient listings of laboratory measurements that meet PCSA criteria will be provided for the report appendix. For those laboratory parameters that don't have an associated PCSA criteria, similar summary tables can be provided based on measurements outside the central laboratory normal ranges, if applicable.

Drug-induced liver injury

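### SAP 6.3 caps a completer's missing last-injection date at week 96, but treatment in this study ends at week 192: a minor correction affecting by-visit laboratory and vital-sign summaries

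*SAP*

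**What the plan says.** SAP 6.2 takes the last-dose date from the injection form, "or missing if the last administration date is unknown". For that case SAP 6.3 imputes the date, in order to fix the start or end of the safety and efficacy analysis periods. It takes the earliest of three candidates:

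- the end of the recorded month, or of the recorded year;
- "the date of the end of treatment visit (week 96 visit for completer", or the early end-of-treatment visit for a patient who stopped treatment prematurely;
- the date of last contact.

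The rest of the plan puts the end of treatment elsewhere. SAP 2.3 states "Visits are planned at weeks 0, 8, 12, 24, 48, 72, 96, 120, 144, 168, and 192". SAP 4.4 defines completion of the 192-week period by "at least 190 weeks of exposure and visit W192 performed". Protocol Table 1 heads the week 192 column "End of Treatment/Early Termination". SAP 1.1 gives 96 weeks as the exposure in the parent study, R727-CL-1532.

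Two planned summaries are expressly limited by the last dose. By-visit laboratory results (SAP 5.7.2) are those "collected up to the day of last dose of study treatment +21 days", and SAP 5.7.3 sets the same limit for vital signs.

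**The concern.** The gloss names a visit halfway through treatment. Because the earliest candidate wins, the error binds: for anyone treated well past week 96, that visit precedes the other two dates. It would even override a partial date whose recorded month and year are later, so known information would be discarded.

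At stake are the later by-visit laboratory and vital-sign data of the affected patients. Those late visits are what a long-term safety extension exists to describe.

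The wording does not look like a deliberate shortening after the early termination on January 31, 2020. The SAP carries a page date of July 16, 2020 and describes that termination. It still keeps analysis windows to week 192 and Kaplan-Meier rates at 144 and 192 weeks. SAP 1.2.3 lists only one change from the protocol's statistical section: all analyses are descriptive.

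**Working it through.** **Inputs**

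- Target days and windows (SAP Appendix 10.1, Table 1): week 96 is day 673, week 120 is day 841, week 192 is day 1345.
- Visit tolerance of ±3 days (protocol Table 1).
- Limit for by-visit summaries: last dose + 21 days (SAP 5.7.2, 5.7.3).
- Scheduled laboratory visits after Day 1 (hematology, chemistry, urinalysis; protocol Table 1): weeks 24, 48, 72, 96, 120, 144, 168, 192, so 8.
- Scheduled vital-sign visits after Day 1: weeks 48, 96, 144, 192, so 4.

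**1. Reproduce the plan's own days.** Study day = 7 × week + 1. Week 96: 7 × 96 + 1 = 673. Week 192: 7 × 192 + 1 = 1345. The formula returns all ten target days in Table 1.

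**2. Find the binding candidate.** For a week-192 completer, last contact is at or after the week 192 visit. The end of the recorded month or year is at or after the true last dose. Week 96 comes before both, so the imputed last dose is no later than about day 673 (670 to 676 with the visit tolerance).

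**3. Limit of the by-visit summaries.** 673 + 21 = day 694 (670 + 21 = 691 to 676 + 21 = 697).

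**4. Visits lost.** The earliest in-window week 120 visit is day 841 − 3 = 838, which is after 697. Laboratory weeks 120, 144, 168 and 192 are lost (4 of 8), as are vital-sign weeks 144 and 192 (2 of 4). The week 96 visit itself, at days 670 to 676, is kept.

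**5. With the correction.** The cap becomes the week 192 visit, day 1345, and the limit is 1345 + 21 = day 1366 (1363 to 1369). Every scheduled visit is kept. The two limits differ by 1366 − 694 = 672 days, or 96 weeks.

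**6. What does not move.**

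- TEAE tables, deaths and PCSA counts use the period in SAP 4.7.1, which ends at the last study visit.
- Last on-treatment values are those "collected during the respective treatment period (as defined in Section 4.7.1"; worst values use the same period.
- Exposure and compliance stay missing when an injection date is missing (SAP 6.3).

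**7. Day 1 in Appendix 10.1.** The introductory text sets Day 1 at the first double-blind dose and labels it baseline. The note under Table 1 counts from the first IMP injection. Counted from the parent study's first dose, this study's week 192 visit would fall at about week 96 + 192 = 288, day 7 × 288 + 1 = 2017. The last window ends at day 1428. Only the first injection in R727-CL-1609 fits the table.

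**The case against.** The strongest reply is that the operative words are the end-of-treatment visit, and that the parenthesis is a leftover from the parent study. Read literally it places the last dose before injections already on record, which a sensible programmer would notice. Using the actual end-of-treatment visit loses nothing. The case should also be rare: "Patients will complete a dosing log to document compliance with study drug administration", the study stopped early, and all results are descriptive. This stands as an argument about size. It does not make the text right. SAP 6.2 foresees an unknown last-dose date, and two programmers following the sentence in good faith could get different tables.

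A second reply also has force. SAP 5.7 and 5.8 say that measurements are assigned to windows to give time points from week 8 to week 96. Read as literally as 6.3, that wording stops by-visit safety summaries at week 96 for every patient, and 6.3 then adds almost nothing. The 4-of-8 and 2-of-4 losses therefore assume that the week 96 limit in 5.7 and 5.8 is itself a leftover and that Table 1 governs.

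A reader might draw four stronger inferences that the documents do not support:

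- **Patients stopped by the sponsor's termination also lose visits.** If treated as completers they would lose 3 of 7 laboratory visits with an end at week 168, 2 of 6 at week 144 and 1 of 5 at week 120. But SAP 6.3 has a separate limb for early end of treatment, under which they lose no scheduled visit. SAP 4.4 lists both a 192-week completer and an eCRF-defined completer, and does not say how these patients are coded.
- **The Week 96 summary is badly cut.** Days 695 to 756 are 62 of the window's 168 days. But SAP 6.4 selects the value nearest day 673, and the week 96 sample is kept, so the cut has almost no effect.
- **The primary endpoint is truncated.** SAP 4.6.1 defines it through last dose plus 2 weeks, but the planned adverse-event tables use the TEAE period, which ends at the last study visit.
- **Time-to-event results change.** SAP 5.8 censors LDL-C events at the end of the treatment period without tying that to last dose. SAP 5.5.1 does not say whether the Kaplan-Meier discontinuation curves use the imputed date.

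**Conclusion.** The contradiction is real and the rule as written gives a wrong date. The loss worked out above applies to a week-192 completer whose last-injection date is missing or partial. It rests on two assumptions: that the parenthesis is programmed as written, and that by-visit summaries are meant to run to week 192. The documents give no count of such patients, and it may be zero. This is a minor correction, not a threat to the study's main safety results.

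**What to change.** 1. **SAP 6.3:** replace the week 96 gloss with the patient's actual end-of-treatment visit in R727-CL-1609, that is week 192, or the final treatment visit at sponsor termination.
2. **SAP 5.7 and 5.8:** change the last time point from week 96 to week 192, to match Table 1 of Appendix 10.1. Read literally, this wording reaches every patient, so it should be corrected at the same time.
3. **SAP Appendix 10.1:** define study Day 1 as the first injection in R727-CL-1609. Delete both the clause that labels Day 1 as baseline and the sentence that justifies it. Changing Day 1 alone would make the first open-label day the baseline, against SAP 5.6.1, 5.7 and 6.1, which place baseline before the first double-blind dose.

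The cost is wording edits in four places (6.3, 5.7, 5.8 and 10.1) before database lock. No new data and no patient burden are involved.

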6.4. Visit Windows for Time Points

Visit windows will be programmatically imposed on those efficacy and safety measures repeatedly collected over the course of the study. These visit windows are derived from the number of days in study, specifically assigning day ranges to mimic the study assessment schedule provided in the protocol. Data analyzed by time point (including efficacy, laboratory safety data, vital signs, physical examinations) will be summarized using the analysis windows given in Appendix 10.1. These analysis windows will be applicable for all analyses, and they are defined to provide more homogeneous data for time point-specific analyses. If multiple valid values of a variable exist within an analysis window, the nearest from the targeted study day will be selected. If the difference is a tie, the value after the targeted study day will be used. If multiple valid values of a variable exist within a same day,

then the first value of the day will be selected when time is available, else the scheduled visit will be selected.

